4. PARTICIPANT ENROLLMENT AND WITHDRAWAL

4.1. Participant Eligibility

All admission criteria (inclusion and exclusion criteria) are numbered sequentially.

4.1.1. Inclusion Criteria

1. Healthy adults \geq 18 years of age at time of enrollment.
2. Vaccinated with an EUA or approved vaccine against COVID-19 \geq 3 months prior to enrollment on study or infection with COVID-19 \geq 3 months prior to enrollment on study.
3. Able to understand and provide a signed informed consent that fulfills the relevant IRB or IEC guidelines.
4. Agrees to the collection of biospecimens (eg, NP swabs) and venous blood per protocol.
5. Ability to attend required study visits and return for adequate follow-up, as required by this protocol.
6. Temperature $< 38^{\circ}\text{C}$.
7. Agreement to practice effective contraception for female participants of childbearing potential and non-sterile males. Female participants of childbearing potential must agree to use effective contraception while on study until at least 1 month after the last dose of vaccine. Non-sterile male participants must agree to use a condom while on study until at least 1 month after the last dose of vaccine. Effective contraception includes surgical sterilization (eg, vasectomy, tubal ligation), two forms of barrier methods (eg, condom, diaphragm), IUDs, oral contraceptives, injectable contraceptives, patches, implants, and abstinence.
8. HIV-positive participants must have been on anti-retroviral therapy for \geq 4 weeks and have HIV-1 viral load $< 1,000$ copies/mL at the time of enrollment.

4.1.2. Exclusion Criteria

1. Serious adverse reaction to any vaccine, any unrelated medication or any component of the investigational vaccine, including a history of anaphylaxis and symptoms of a severe allergic reaction and history of allergies in the past.
2. Confirmed current COVID-19, SARS-CoV-2 infection in the last < 3 months, or PCR positive for SARS-CoV-2 at screening.
3. Vaccinated with an EUA or approved vaccine against COVID-19 in the last < 3 months.
4. Pregnant or breastfeeding women.
5. Any participants with a history of myocarditis or pericarditis.
6. Chronic lung disease (included COPD) as evidenced by one or more exacerbations requiring a course of steroids in the last year, or the requiring chronic low dose oral steroids to prevent exacerbations. Uncontrolled asthma, defined as requiring reliever

inhaler (short-acting beta agonist or ipratropium bromide) more than twice a week is also excluded.

7. Bone marrow or organ transplant recipient
8. Extreme obesity (defined as BMI of 40 kg/m² or higher).
9. Chronic kidney disease requiring dialysis.
10. History of liver disease.
11. Any disease associated with acute fever, or any infection.
12. Participants with acquired or hereditary immunodeficiencies other than well-controlled HIV are excluded from enrollment.
13. Current diagnosis of active tuberculosis.
14. History of hereditary, idiopathic or acquired angioedema.
15. No spleen or functional asplenia.
16. Chronic use (more than 14 continuous days) of any medications that may be associated with impaired immune responsiveness including, but not limited to, systemic corticosteroids exceeding 10 mg/day of prednisone equivalent, allergy injections, immunoglobulin, interferon, or immunomodulators. The use of low dose topical, ophthalmic, inhaled and intranasal steroid preparations will be permitted.
17. According to the judgement of the investigator any medical, psychiatric, psychological, social, occupational or other conditions that could affect the participants ability to sign informed consent, provide safety assessment data or comply with the requirements of the study protocol.
18. Assessed by the Investigator to be unable or unwilling to comply with the requirements of the protocol.

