8.2. Analysis Population(s)

The following analysis populations are defined:

Population	Definition
Modified Intent-to-Treat (mITT)	All randomized participants who receive at least one dose of vaccine. Participants will be analyzed according to their randomized arm.
Safety	All randomized participants who receive at least one dose of vaccine. Participants will be analyzed according to the actual study intervention received. The Safety Population will be used for all safety analyses.
Immunogenicity	All randomized participants who received at least one dose of vaccine with at least 1 valid follow-up assessment immunogenicity result. Participants will be analyzed according to the actual study intervention received. The Immunogenicity Population will be used for the phase 1 and 2 immunogenicity analyses.

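### Exclusions 3 and 16 let in participants with a recent investigational COVID-19 vaccine or a single or short course of an antibody product, and their titres stay in the antibody GMTs; the effect is probably small

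*Combined protocol and SAP*

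**What the plan says.** Inclusion 2 (Section 4.1.1) admits people whose authorised or approved COVID-19 vaccination, or whose infection, lies at least 3 months back. Three exclusions in Section 4.1.2 bear on recent exposure:

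- Exclusion 2: "Confirmed current COVID-19, SARS-CoV-2 infection in the last < 3 months, or PCR positive for SARS-CoV-2 at screening".
- Exclusion 3: "Vaccinated with an EUA or approved vaccine against COVID-19 in the last < 3 months".
- Exclusion 16: "Chronic use (more than 14 continuous days) of any medications that may be associated with impaired immune responsiveness including", followed by a list that names "allergy injections, immunoglobulin, interferon, or immunomodulators".

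Exclusion 17 gives the investigator discretion, but only over conditions that bear on a participant's "ability to sign informed consent, provide safety assessment data or comply with the requirements of the study protocol".

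The GMTs of S- and N-specific IgG and of neutralizing antibody are phase 2 primary endpoints (Section 3.4.2.1) and phase 1 secondary endpoints (Section 3.4.1.2). They are computed on the Immunogenicity population of Section 8.2: "All randomized participants who received at least one dose of vaccine with at least 1 valid follow-up assessment immunogenicity result". Section 8.3.3 gives a GMT with a 95% confidence interval at each time point. Section 8.3.1 rules out statistical comparison of the phase 2 arms.

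**The concern.** Exclusions 2 and 3 keep out people infected, or vaccinated with an authorised product, within 3 months. No such limit applies to two other recent sources of antibody: a COVID-19 vaccine still under investigation, and antibody given directly as immunoglobulin, plasma or an anti-SARS-CoV-2 product. The binding and neutralization assays of Section 6.6.1.1 measure antibody in the sample and do not show where it came from.

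Because phase 2 is descriptive, the GMTs and their intervals are themselves the result. Antibody brought in from outside the study would be reported as part of an arm's or cohort's response.

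**Working it through.** **Step 1. Eligibility, case by case.**

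- *Recent investigational vaccine.* Take someone infected well over 3 months ago who received an investigational COVID-19 vaccine a few weeks before day 1. Inclusion 2 is met through the infection. Exclusion 2 does not apply, and exclusion 3 does not apply because the product is neither authorised nor approved. None of the 18 exclusions mentions other trials or investigational products.
- *Single or short course of immunoglobulin.* Exclusion 16 needs chronic use beyond 14 continuous days, so this course does not meet it.
- *Single dose of plasma or anti-SARS-CoV-2 antibody.* Neither is named in any criterion. If it was given to treat an infection within 3 months, exclusion 2 bars the person. If it was given preventively, nothing does.

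**Step 2. Later safeguards.** Vaccination history is recorded at screening (Section 6.7.1.1) and concomitant medications from consent onward (Section 6.8). No rule in the available text acts on either for this purpose. Section 8.2 requires only a dose and one valid follow-up result, and Section 8.3.3 states no baseline adjustment.

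**Step 3. Size.** The plan has no figure of its own to reproduce: Section 8.4 says that the sample sizes have no statistical justification. The inputs from the documents are n = 30 per phase 2 arm and n = 10 per phase 1 cohort. The fold increase f is an assumption.

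The log GMT is the mean of the log titres. Raising one titre f-fold adds log(f)/n to that mean, so the GMT is multiplied by f^(1/n).

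| f (assumed) | n = 30 | n = 10 |
|---|---|---|
| 2 | 2^(1/30) = 1.02 | 2^(1/10) = 1.07 |
| 4 | 4^(1/30) = 1.05 | 4^(1/10) = 1.15 |
| 10 | 10^(1/30) = 1.08 | 10^(1/10) = 1.26 |

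With three affected people in one arm of 30 and f = 10, the multiplier is 10^(3/30) = 1.26.

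**Step 4. Comparison with sampling error.** The 95% interval of a GMT extends 10^(t × SD/√n)-fold each way. The documents give no SD, so take a log10 SD of 0.3 to 0.7 (assumption).

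- n = 30, t = 2.045: 10^(2.045 × 0.3/√30) = 1.29, up to 10^(2.045 × 0.7/√30) = 1.83.
- n = 10, t = 2.262: 10^(2.262 × 0.3/√10) = 1.64, up to 10^(2.262 × 0.7/√10) = 3.17.

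One affected participant moves the GMT by less than this in both settings.

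**Step 5. How likely.** The documents give no prevalence. The chance of at least one affected person in an arm of 30 is 1 − (1 − p)^30. At assumed p of 1%, 2% and 5% this is about 26%, 45% and 79%. The binomial chance of three or more is about 0.3%, 2% and 19%.

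**The case against.** The strongest case against is that the gap is narrow and its effect lies inside the noise. Inclusion 1 asks for healthy adults, exclusion 7 removes transplant recipients, and exclusion 12 removes immunodeficiency other than well-controlled HIV. What remains is sporadic or preventive use in otherwise healthy people, and that is probably uncommon. Everyone enrolled already has antibody from vaccination or infection by design, and ordinary immunoglobulin is not shown in the documents to raise these titres. Phase 2 is randomized with no between-arm test. A day 1 pre-dose sample (Table 10) and the vaccination history could reveal affected people. All of this stands and limits the weight of the point. It does not close the gap, because the rules followed exactly still admit such participants and keep them in the analysis.

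Stronger conclusions that a reader might draw are not supported:

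- *That immunoglobulin is never excluded.* Ongoing therapy is caught on a natural reading of chronic use. The list also names allergy injections, which suggests that the 14 days describe the length of a regimen rather than daily dosing.
- *That a course taken years ago excludes, because exclusion 16 has no date.* Other exclusions say so when they look back, so undated chronic use most naturally means current use. Adding a date would be a clarification only.
- *That the measured rise is lowered.* No fold-rise is planned; the endpoints are GMTs at each time point.
- *That one arm is favoured.* Randomization makes chance imbalance the likelier result.
- *That the distortion is large.* A 100-fold titre would give 100^(1/30) = 1.17 and 100^(1/10) = 1.58, but nothing in the documents supports that input for people already primed and then boosted.

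**Conclusion.** The gap is real but of modest consequence. Exclusion 3 misses investigational COVID-19 vaccines, exclusion 16 misses single or short-course antibody products, and Section 8.2 does not remove the people concerned from the antibody GMTs. The ELISpot endpoint is not an antibody measure and is not part of this point.

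With one affected participant at an assumed 2- to 10-fold increase, the GMT shifts by about 2% to 8% in a phase 2 arm and about 7% to 26% in a phase 1 cohort. The larger figure applies where immunogenicity is secondary. A shift of 26% in a phase 2 arm would need about three people affected at 10-fold in the same arm. The fold increase, the SD and the prevalence are all assumptions.

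The exclusion list is complete, numbered 1 to 18, so its silence can be relied on. Parts of Section 5 are not in the available text, so a medication rule elsewhere cannot be ruled out. The correction is worth making because it is cheap, not because the bias is likely to be large.

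**What to change.** 1. In exclusion 3, replace the restriction to authorised or approved products with any COVID-19 vaccine, including an investigational one. The existing 3-month limit stays.
2. Add a separate exclusion for any receipt, including a single dose, of immunoglobulin, plasma or anti-SARS-CoV-2 antibody within a stated interval before day 1. The sponsor should set the interval, since the documents give no basis for choosing one for these products.

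The cost is a change to the eligibility wording and one screening question, because vaccination and medication history are already taken. The downside is a few extra screen failures.

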4.2. Strategies for Recruitment and Retention

Clinical study sites have been chosen based on their previous experience and infrastructure.

Site staff are responsible for ensuring that participants attend their regularly scheduled treatment visits.

4.3. Screen Failures

Participants who sign a screening informed consent form (ICF) but who do not meet all of the eligibility criteria will be considered screen failures. Data on screen failures will not be entered into the Electronic Data Capture (EDC) system for the purposes of the study. ICFs and screening source documents will be maintained as part of the study file with the eligibility failure reason clearly documented.

4.4. Withdrawal of Participants

A participant may voluntarily discontinue study participation at any time. At the Investigator's discretion, participants may be discontinued or withdrawn from the study at any time after discussion with the Investigator and Medical Monitor.

4.5. Treatment Discontinuation

Participant treatment must be discontinued if any of the following occur:

- Unacceptable toxicity/AE.
- Withdrawal of consent.
- Participant noncompliance.
- Pregnancy or currently nursing.
- Administrative decision by the Investigator or Sponsor.

Participants who are withdrawn from this study secondary to a laboratory toxicity or AE should be followed by the Investigator as outlined in [Section 7](#).

4.6. Replacement of Participants

In phase 1, no participants who are vaccinated will be replaced. In phase 2, participants who are randomized to either the control or experimental arm will not be replaced.

4.7. Premature Termination or Suspension of Study

This study may be temporarily suspended or prematurely terminated if there is sufficient reasonable cause. Written notification, documenting the reason for study suspension or termination, will be provided by the suspending or terminating party to the Investigators and the regulatory authorities. If the study is prematurely terminated or suspended, the Principal Investigator will promptly inform the IRB and will provide the reason(s) for the termination or suspension.

Circumstances that may warrant termination or suspension include, but are not limited to:

- Death that is suspected to be related to the treatment regimen
- Determination of unexpected, significant, or unacceptable risk to participants
- Insufficient compliance to protocol requirements
- Data that are not sufficiently complete and/or evaluable

The study may resume once concerns about safety, protocol compliance, and data quality are addressed and satisfy the Sponsor, the IRB, and/or the South African Health Products Regulatory Authority (SAHPRA).

AAHI-SC2 and AAHI-SC3

Clinical Trial Protocol: COVID-4.015 Version 4

ImmunityBio, Inc.

5. TREATMENT PROCEDURES

AAHI-SC2 and AAHI-SC3

Clinical Trial Protocol: COVID-4.015 Version 4

ImmunityBio, Inc.

5.1.5. Dosing and Administration

Participants will be administered vaccine in each study phase as described in [Section 3.1](#). Participants will be monitored for 30 minutes after each administration for immediate adverse reactions (ARs), and appropriate personnel and therapies will be available to respond to any immediate AR.

Toxicity study stopping rules are detailed in [Section 7.8.2](#).

5.1.6. Accountability of IP

The Investigator or designee(s) must maintain an inventory record of IP received, administered, returned, and discarded in the IP accountability record as detailed in the Pharmacy Manual. IP accountability records must be made available to the Sponsor or designated monitoring personnel for the purpose of conducting drug accountability.

Unused portions of IP are not to be stored or subsequently used and will need to be properly disposed of in accordance with institutional policy and procedure, and disposal must be recorded on the IP accountability record.

5.1.7. Management of Adverse Events and Individual Stopping Criteria

Participants will be monitored for 30 minutes after each administration for immediate adverse reactions ARs, and appropriate personnel and therapies will be available to respond to any immediate AR. Participants will also be monitored for adverse reactions throughout the study per the schedule of events listed in [Table 10](#). Discussion of toxicities that may warrant stopping the study are detailed in [Section 7.8.2](#).

Approved

6. STUDY PROCEDURES AND EVALUATIONS

All required study procedures and evaluations are to be conducted as outlined in this protocol. In the event of a deviation from the protocol due to an emergency, accident, or mistake, the Investigator or designee must notify the Sponsor as soon as possible.

All laboratory assessments and evaluations will be performed locally. Procedures and evaluations to be performed are detailed in the schedules of events shown in [Table 10](#).

6.1. Prescreening Assessments

If possible, the prescreening visit should occur on the same day as and immediately prior to the screening visit. The assessments to be performed in the prescreening visit include:

- Study introduction and written informed consent for prescreening obtained prior to performing any study assessments or procedures
- Blood draw for SARS-CoV-2 testing
- Blood draw for HIV testing

SARS-CoV-2 and HIV testing will use rapid testing assays.

6.2. Baseline/Screening Assessments

The following procedures and evaluations are to be performed at baseline/screening:

- Study introduction and written informed consent obtained prior to performing any study assessments or procedures (screening visit and/or protocol amendments that affect study assessments or participant treatment).
- Inclusion/exclusion
- Demographics and complete medical history, including current symptoms and COVID-19-related symptoms
- Tuberculosis screening
- History of COVID-19
- Confirmation of contraceptive measures
- Physical exam
- Vital signs
- Concomitant medications
- Blood draw and urine collection for clinical laboratories
- Biospecimen collection for SARS-CoV-2 testing
- Pregnancy test (serum [β -human chorionic gonadotropin] or urine): The pregnancy test result will be confirmed as negative immediately prior to vaccine administration. A positive pregnancy test occurring while the participant is participating in the study is considered an immediately reportable event.

6.3. Safety Assessments

All participants will be monitored for AEs during the study. Assessment of AEs will include the following parameters:

- All MAAEs and SAEs for 6 months after last vaccine administration (related MAAEs and SAEs at any time)
- Solicited local and systemic AEs via diary for 7 days after each vaccine administration (applicable to the phase 1 and phase 2 studies)
- Unsolicited AEs via diary from first dose of study treatment until 30 days after last vaccination (applicable to the phase 1 and phase 2 studies)
- Vital signs
- Body weight
- Physical examinations
- Hematology: CBC with differential
- Chemistry panel: Collection of whole blood for complete metabolic panel (CMP)
- Urinalysis: protein, glucose, and RBCs
- Pregnancy test.

6.3.1. Solicited Local and Systemic Adverse Events

Solicited AEs will be captured at study visits and by a diary distributed to participants. Thermometers and rulers will be provided to participants for evaluating AEs. Text and/or phone reminders to complete the solicited AE diary may be provided to participants.

Solicited local AEs to be assessed include redness, firmness, swelling, pain or itching at the injection site, medication taken for pain after IM administration, tingling/numbness, and bleeding or bruising at the injection site after IM administration. Solicited systemic AEs to be assessed include chills, nausea, vomiting, diarrhea, headache, fatigue, myalgia, abdominal discomfort/pain, joint pain, and fever. The solicited AE diary may be either electronic diary (eDiary) or a paper diary, as available. A sample diary for collecting solicited AEs is provided in [Appendix 1](#).

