7. ADVERSE EVENT MONITORING AND REPORTING

AEs will be recorded and monitored and, when appropriate, reported to SAHPRA and others involved in an investigation (sponsors, IRBs, and investigators) in accordance with existing statutes. In addition, to assist in monitoring safety and making required reports, AEs will be categorized in accordance with the Guidance for Industry: Toxicity Grading Scale for Healthy Adult and Adolescent Volunteers Enrolled in Preventive Vaccine Clinical Trials (2007). These scales are described in more detail in the following sections.

7.1. Guidance for Industry: Toxicity Grading Scale for Healthy Adult and Adolescent Volunteers Enrolled in Preventive Vaccine Clinical Trials (2007)

The enrollment of healthy volunteers warrants a very low tolerance for risk. The Guidance for Industry: Toxicity Grading Scale for Healthy Adult and Adolescent Volunteers Enrolled in Preventive Vaccine Clinical Trials (2007) will be used to assess the severity of clinical and laboratory abnormalities in healthy adult volunteers enrolled in this study. AEs will be graded according to the following tables from The Guidance for Industry: Toxicity Grading Scale for Healthy Adult and Adolescent Volunteers Enrolled in Preventive Vaccine Clinical Trials (2007).

Table 11: Clinical Abnormalities: Local Reaction to Injectable Products

Local Reaction to Injectable Product	Mild (Grade 1)	Moderate (Grade 2)	Severe (Grade 3)	Potentially Life Threatening (Grade 4)
Pain	Does not interfere with activity	Repeated use of non-narcotic pain reliever > 24 hours or interferes with activity	Any use of narcotic pain reliever or prevents daily activity	Emergency room (ER) visit or hospitalization
Tenderness	Mild discomfort to touch	Discomfort with movement	Significant discomfort at rest	ER visit or hospitalization
Erythema/Redness *	2.5 – 5 cm	5.1 – 10 cm	> 10 cm	Necrosis or exfoliative dermatitis
Induration/Swelling **	2.5 – 5 cm and does not interfere with activity	5.1 – 10 cm or interferes with activity	> 10 cm or prevents daily activity	Necrosis

* In addition to grading the measured local reaction at the greatest single diameter, the measurement should be recorded as a continuous variable.

** Induration/Swelling should be evaluated and graded using the functional scale as well as the actual measurement.

Table 12: Clinical Abnormalities: Vital Signs

Vital Signs *	Mild (Grade 1)	Moderate (Grade 2)	Severe (Grade 3)	Potentially Life Threatening (Grade 4)

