7.2. Definition of Adverse Events

AEs and grading criteria listed below are consistent in definitions in 21 CFR 312.32.

An AE is any noxious, unintended, or untoward medical occurrence that may appear or worsen in a participant during the study. It may be a new intercurrent illness, a worsening concomitant illness, an injury, or any concomitant impairment of the participant's health, including laboratory test values (as specified by the criteria below), regardless of etiology. A diagnosis or syndrome should be recorded on the AE page of the case report form (CRF) rather than the individual signs or symptoms of the diagnosis or syndrome.

An abnormal laboratory value is considered to be an AE if the abnormality:

- Results in discontinuation from the study;
- Requires treatment, modification/interruption of the study treatment dose, or any other therapeutic intervention; or
- Is judged to be of significant clinical importance.

Regardless of the severity grade, only laboratory abnormalities that fulfill a seriousness criterion need to be documented as an SAE.

If a laboratory abnormality is one component of a diagnosis or syndrome, then only the diagnosis or syndrome should be recorded as an AE. If the abnormality was not a part of a diagnosis or syndrome, then the laboratory abnormality should be recorded as an AE.

An AE with medically-attended visits (either in person or telemedicine visit) that are not routine visits for physical examination or vaccination, such as visits for hospitalization, an emergency room visit, or an otherwise unscheduled visit to or from medical personnel (medical doctor) for any reason, will be documented as a MAAE. MAAEs can also be SAEs and will follow the same serious adverse event criteria and collection guidelines noted in [Section 7.3](#).

Duration and Frequency for Collecting AE and SAE Information

In the phase 1 and phase 2 studies, solicited AEs will be recorded by the investigator for 7 days after each dose. In the phase 1 and phase 2 studies, unsolicited AEs will be recorded from the time of first dose of study treatment until 30 days after study intervention. All MAAEs and SAEs will be recorded by the investigator from the time of first dose of study treatment until 6 months after study intervention. For MAAEs/SAEs that are considered related to study treatment, those events should be reported at any time regardless of vaccine administration date or end of study visit date.

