8.3.2. Analyses of Safety

Safety analyses will be summarized with descriptive statistics and performed on the Safety population.

For all phases, safety will be assessed by the incidence of treatment-emergent MAAEs, SAEs, solicited local and systemic reactogenicity AEs, and unsolicited AEs for the time period of interest, overall and by grade according to the Guidance for Industry: Toxicity Grading Scale for Healthy Adult and Adolescent Volunteers Enrolled in Preventive Vaccine Clinical Trials (2007). Clinically significant changes in safety laboratory tests and vital signs will be summarized.

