APPENDIX 1. SAMPLE DIARY FOR SOLICITED EVENTS

STUDY NUMBER*: _____

Patient Number*		Date of Vaccine Administration	/	/	/	*To be completed by the site		
-----------------	--	--------------------------------	---	---	---	------------------------------	--	--

Please answer all questions below daily for 7 days, beginning with day of treatment. Be sure to bring back this completed diary to your next clinic visit.

Intramuscular: Solicited local AEs	Instructions	Date / /						
1. Is there redness at the injection site?	Check:  Yes or  No If yes, measure longest diameter in cm	 Yes or  No _____ cm	 Yes or  No _____ cm	 Yes or  No _____ cm	 Yes or  No _____ cm	 Yes or  No _____ cm	 Yes or  No _____ cm	 Yes or  No _____ cm
2. Is there firmness at the injection site?	Check:  Yes or  No	 Yes or  No	 Yes or  No	 Yes or  No	 Yes or  No	 Yes or  No	 Yes or  No	 Yes or  No
3. Is there swelling at the injection site?	Check:  Yes or  No If yes, measure longest diameter in cm	 Yes or  No _____ cm	 Yes or  No _____ cm	 Yes or  No _____ cm	 Yes or  No _____ cm	 Yes or  No _____ cm	 Yes or  No _____ cm	 Yes or  No _____ cm

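### Section 6.3.1 lists taking pain medication as a solicited local adverse event, although Table 11 uses it to grade pain, and the diary's pain key leaves it out

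*Combined protocol and SAP*

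**What the plan says.** Section 6.3.1 gives the solicited local list: "Solicited local AEs to be assessed include redness, firmness, swelling, pain or itching at the injection site, medication taken for pain after IM administration". The list continues with tingling or numbness, bleeding and bruising. In Appendix 1, item 5 of the local page is a separate daily Yes/No question on medication for injection-site pain or itching, with space for the product name.

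Section 7.2 defines the term: "An AE is any noxious, unintended, or untoward medical occurrence that may appear or worsen in a participant during the study".

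Table 11 (Section 7.1) grades injection-site pain partly by analgesic use. Grade 2 is "Repeated use of non-narcotic pain reliever > 24 hours or interferes with activity" and Grade 3 is "Any use of narcotic pain reliever or prevents daily activity". The key printed in Appendix 1 for injection-site pain or itching has three levels, all based on limitation of activity. It does not mention analgesics.

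Incidence and severity of solicited local events in the week after each vaccination is a primary endpoint in phase 1 (Section 3.4.1.1) and a secondary endpoint in phase 2 (Section 3.4.2.2.1). Section 8.3.2 reports incidence "overall and by grade", using the Guidance scale.

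**The concern.** An item that only records how a participant treated a symptom stands in the list of events. If the tables are programmed from that list, a treated painful arm contributes a pain event and a medication event, and the second is not an untoward occurrence at all. The information that Table 11 needs to grade the pain is then used to add an event rather than to set a grade.

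The diary makes this worse, because participants rate pain on a key without the analgesic criteria. Two pain scales therefore sit in one protocol. At stake are the item-level counts and severity distribution of a phase 1 primary endpoint, and the pain grade that enters the pause criteria.

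**Working it through.** The plan has no figure to reproduce. Section 8.4 says that the sample sizes have no statistical basis, and no reactogenicity rates are given. The check compares the texts and adds a small illustration.

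**Step 1. Is medication use an event?** Section 7.2 requires an untoward medical occurrence. Taking an analgesic is a response to one. Table 11 agrees: it has no medication row and puts analgesic use inside the pain row at Grades 2 and 3.

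**Step 2. Effect on the count.** Let n be the group size, p the share with injection-site pain, and m the share of those who medicate.

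- Participants with pain = n × p
- Listed events (pain plus medication) = n × p × (1 + m)

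Group sizes come from Section 8.4 (10 per phase 1 cohort, 30 per phase 2 arm). The values of p and m are assumptions.

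| n | p | Participants with pain | Listed events at m = 10% / 30% / 50% |
|---|---|---|---|
| 10 | 50% | 5.0 | 5.5 / 6.5 / 7.5 |
| 10 | 80% | 8.0 | 8.8 / 10.4 / 12.0 |
| 30 | 50% | 15.0 | 16.5 / 19.5 / 22.5 |
| 30 | 80% | 24.0 | 26.4 / 31.2 / 36.0 |

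The ratio is 1 + m, so 1.1 to 1.5 over this range. The number of participants with any local event stays at n × p when everyone who medicates also reports pain (other local symptoms aside), because each person is counted once.

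**Step 3. Effect on the grade.** Take two diary records in which the participant circles Mild for pain.

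- Non-narcotic analgesic on 3 consecutive days: the diary key gives Mild. Table 11 gives Grade 2, because use is repeated over more than 24 hours.
- One dose of a narcotic analgesic: the diary key gives Mild. Table 11 gives Grade 3.

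The omission looks unintended. The diary's headache key does include the analgesic criteria and matches the headache row of Table 13.

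**Step 4. Link to the pause criteria.** Section 7.8.2 counts 3 or more participants with the same or similar related Grade 3 solicited event. Section 7.8.2.1 counts 3 or more with a related event of Grade 3 or above. Suppose three participants in a cohort have related Grade 3 pain under Table 11, one of them only through narcotic use. If that one keeps the self-rating of Mild, the count is 3 − 1 = 2 and the criterion is not met on this event.

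**The case against.** The strongest reply is that Section 6.3.1 is a collection list and not a counting rule. It says what is to be assessed, and Section 8.3.2 does not say that every diary Yes becomes an event. Section 8.1 leaves detail to a SAP, and the text available here contains no derivation. Lacking a Table 11 row is also no defect in itself: itching, tingling, bleeding and bruising have none and are still legitimately solicited. All this is fair. It does not explain why medication use is named as an adverse event in Section 6.3.1, and that listing is explicit.

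On grading, Sections 7.4 and 7.4.1 have a qualified investigator grade events by the Guidance scale, and the diary records medication by name each day. A reader might infer that pain will be under-graded. The documents support only a risk of that, since the investigator can correct the self-rating. However, no text says that item 5 must be used to do so.

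A reader might also infer that redness and swelling of any size are counted, so that local incidence is inflated. The diary does ask "1. Is there redness at the injection site" with no minimum size, while the size ranges in Table 11 start at 2.5 cm. But no section says that smaller reactions enter the incidence. The diameter is recorded, so a cut-off can be applied at analysis. Swelling does not depend on size alone: Grade 1 is "2.5 – 5 cm and does not interfere with activity", but Grade 2 is "5.1 – 10 cm or interferes with activity". Nor does the general scale in Section 7.4.1 turn a small red spot into Grade 1, because it covers only events that the Guidance does not define. Any inflation factor would merely restate an assumed distribution of diameters. What remains is a request to state how reactions below Grade 1 are tabulated.

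Finally, the phase 2 arms are not formally compared (Section 8.3.1), so no test result depends on this.

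**Conclusion.** The point holds for medication use and pain grading. Section 6.3.1 and diary item 5 list as a solicited local event something that Section 7.2 does not make an event and that Table 11 uses to grade pain. Read literally, item-level local events rise by the factor 1 + m, which is 1.1 to 1.5 if 10–50% of those with pain medicate. That range is assumed, and the result requires that listed items are tabulated as events.

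The participant-level rate of any local event is unaffected when pain or itch is also reported. Under-grading of pain is possible but not certain. It matters beyond the tables because pain grade enters the Grade 3 pause criteria. The documents do not establish a miscount of redness or swelling.

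**What to change.** 1. In Section 6.3.1, remove medication taken for pain from the list of solicited local adverse events. In Appendix 1, keep it as a diary item.
2. Split diary item 5 so that medication for pain is recorded separately from medication for itch. As printed, treated itch could be read as a reason to raise a pain grade.
3. Reconcile the Appendix 1 pain key with the pain row of Table 11, and state in Section 8.3.2 or the SAP that reported pain grades follow Table 11 using the recorded medication.
4. Add one sentence on how redness and swelling below Grade 1 are tabulated. This is a clarification only.

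The cost is a sentence in Section 6.3.1, one small diary edit and a short derivation rule. The downside is that some pain grades may rise. Diaries already completed on the present form will not separate pain from itch medication, so those records would need the investigator's judgement.
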